10.5.8.2. Eliciting, Recording, and Reporting Adverse Events

10.5.8.2.1. Eliciting Adverse Events

Subjects will be instructed that they may report AEs at any time. An open-ended or nondirected method of questioning should be used at each study visit to elicit the reporting of AEs.

10.5.8.2.2. Recording Adverse Events

The AE reporting period for safety surveillance begins when the subject is initially included in the study (date of first signature of informed consent) and continues up to 30 days after the last study drug administration. If an AE is not resolved or stabilized by this time, the Sponsor in consultation with the Investigator will decide whether to continue to monitor the AE or closeout the event in the database if no further follow-up is necessary.

Any SAE suspected to be related to the study drug must be reported whenever it occurs, irrespective of the time elapsed since the last administration.

Investigator and study personnel will record all AEs and SAEs whether received through an unsolicited report by a subject, elicited during subject questioning, discovered during physical examination, laboratory testing, and/or other means by recording them on the eCRF and SAE Report Form, as appropriate. The following information should be recorded on the AE eCRF:

- Description including onset and resolution dates
- Whether it met SAE criteria
- Severity
- Relationship to study drug or other causality
- Action taken with study drug

- Outcome

For SAEs, events occurring secondary to the primary event should be described on the SAE Report Form in the narrative description field.

The following should be considered when recording SAEs:

- Death is an outcome of an event. The event that resulted in the death should be recorded and reported on the SAE Report Form and eCRF.
- For hospitalizations, surgical, or diagnostic procedures, the illness leading to the surgical or diagnostic procedure should be recorded as the SAE, not the procedure itself. The procedure should be captured in the narrative as part of the action taken in response to the illness.

10.5.8.2.3. Diagnosis Versus Signs or Symptoms

In general, the use of a unifying diagnosis is preferred to the listing out of individual symptoms. Grouping of symptoms into a diagnosis should only be done if each component sign and/or symptom is a medically confirmed component of a diagnosis as evidenced by standard medical textbooks. If any aspect of a sign or symptom does not fit into a classic pattern of the diagnosis, report the individual symptom as a separate AE.

10.5.8.3. Reporting Serious Adverse Events

All SAEs are subject to reporting requirements.

10.5.8.3.1. Serious Adverse Events

All SAEs, whether or not considered related to study drug, must be reported to the Sponsor Contact **within 24 hours of becoming aware of the event**. In addition, a completed report using the Sponsor's SAE Report Form must be submitted within 24 hours of awareness to the designated Sponsor Contact.

PPD

If additional follow-up information is required or becomes available for a previously reported SAE, the new information should be reported to the designated Sponsor Contact **within 24 hours of awareness**.

Elective hospitalization and/or surgery for clearly pre-existing conditions (eg, a surgery that has been scheduled prior to the subject's entry into the study) will not be reported as an SAE.

Any SAE that is ongoing when the subject completes the study or discontinues the study will be followed by the Investigator until the event resolves, stabilizes or returns to Baseline status.

10.5.8.3.2. Serious, Unexpected Adverse Drug Reactions

All ADRs that are both serious and unexpected are subject to expedited reporting to regulatory agencies. An unexpected ADR is one for which the nature or severity is not consistent with information in the relevant source documents.

The following documents or circumstances will be used to determine whether an AE/ADR is expected:

1. For a medicinal product not yet approved for marketing in a country, the RSI section of the company's IB will serve as the source document in that country.
2. Reports that add significant information on specificity or severity of a known, already documented serious ADR constitute unexpected events. For example, an event more specific or more severe than described in the RSI in the IB would be considered "unexpected".

10.5.9. Pregnancy

If at any point any pregnancy test is confirmed positive, the subject will be withdrawn from the study drug.

Details of all pregnancies in female subjects and female partners of male subjects will be collected after the start of study drug and until 30 days after the last dose.

Pregnancy (during maternal or paternal exposure to study drug) does not meet the definition of an AE; however, to fulfill regulatory requirements, any pregnancy and/or pregnancy outcome should be reported via the Pregnancy Report Form to the designated Sponsor Contact **within 24 hours of awareness** to collect data on the pregnancy and on the outcome for both the mother and the fetus.

Abnormal pregnancy outcomes (eg, spontaneous abortion, fetal death, stillbirth, congenital anomalies, ectopic pregnancy) are considered SAEs and should be reported as such even if outside the SAE reporting period.

10.6. Procedures for Overdose

The current version of the IB should be referenced for overdose procedures.

There is no established overdose threshold for this clinical study, nor is there any recommended specific treatment for an overdose but to provide supportive care if clinically indicated.

In the event of a suspected overdose, the Investigator and/or treating physician should:

1. Closely monitor the subject for any AE/SAE and laboratory abnormalities and follow AE reporting process, including contacting the Medical Monitor.
2. Obtain a plasma sample for PK analysis within 7 days from the date of the last dose of study drug, if possible, and if requested by the Medical Monitor.
3. Document the total quantity of the excess dose, taking into consideration the duration of the overdose in the eCRF and the time frame.

Subjects who overdose will be counseled on correct dosing and administration of study drug. Decisions regarding study discontinuation, dose interruptions, or dose modifications will be

made by the Investigator in consultation with the Medical Monitor based on the clinical evaluation of the subject.

11. PLANNED STATISTICAL METHODS

11.1. General Considerations

Statistical considerations will be discussed in Section 11.2 to Section 11.9 for the Double-Blind Treatment Period, and in Section 11.10 for the Open-Label Extension Period. An analysis of efficacy and safety data will be performed after all subjects have completed or early terminated from the 24-week Double-Blind Treatment Period. A final analysis of efficacy and safety data will be performed once all subjects completed or early terminated from the study. Details regarding the statistical analyses will be provided in the Statistical Analysis Plan (SAP), which will be finalized prior to database lock of the double-blind portion of the study.

Continuous variables will be summarized using the number of observations, mean, standard deviation (SD), median, minimum, and maximum. Categorical variables will be summarized using frequency counts and percentages.

All summaries, statistical analyses, and individual subject data listings described in this section will be produced using SAS[®] (Version 9.4 or later; SAS Institute, Inc. Cary, NC).

11.2. Determination of Sample Size

Subjects will be randomized as follows:

- Cohort 1: 36 subjects in 2:1 randomization ratio (24 subjects to etrasimod 2 mg and 12 subjects to placebo)
- Cohort 2: 42 subjects with SALT I < 95 at Baseline in 4:1:2 randomization ratio (24 subjects to etrasimod 3 mg, 6 subjects to etrasimod 2 mg, and 12 subjects to placebo)

Assuming a 15% drop-out rate from the study over 24 weeks, at least 35 treatment completers (20 subjects to etrasimod 3 mg, 5 subjects to etrasimod 2 mg, and 10 subjects to placebo from Cohort 2; plus subjects from Cohort 1 with SALT I < 95 at Baseline) at Week 24 will provide at least 80% and 47% power to detect a treatment difference of 20% for etrasimod 3 mg and etrasimod 2 mg from placebo, respectively, in the percent change from Baseline in SALT I at Week 24 by a 2-sample t-test using a 2-sided significance test level of 0.05 and common standard deviation (SD) of 17.8%.

11.3. Analysis Sets

For purposes of analysis, the following analysis sets are defined (Table 9).

Table 9: Analysis Sets

Analysis Set	Description
Randomized Set	The Randomized Set includes all randomized subjects, irrespective of whether they received any study drug.
Full Analysis Set (FAS)	The FAS includes all randomized subjects with a SALT I < 95 at Baseline, irrespective of whether they received any study drug.
Modified Full Analysis Set (mFAS)	The mFAS consists of all randomized subjects with a SALT I < 95 at Baseline who received at least 1 dose of study drug, have a Baseline measurement, and have at least 1 post-randomization measurement. The mFAS is endpoint specific, therefore subjects included in the analysis set for 1 endpoint may differ from another endpoint, based on the Baseline and post-Baseline data.
Per Protocol Set	The Per Protocol Set consists of all subjects in the FAS who adhere to the protocol. The Per Protocol Set will be used in sensitivity analyses of the primary and key secondary endpoints to evaluate the influence of major protocol violators and protocol deviators on the primary results. Subjects may be excluded from this set if they violate the eligibility criteria or significantly deviate from the study plan. Specific reasons for warranting exclusion from this set will be documented prior to database lock and may include, but are not limited to, study drug noncompliance, receiving incorrect study drug, missing more than a defined number of visits while still on study, and chronic prohibited medication use while on study drug. The list of major protocol violations and protocol deviations that exclude subjects from the Per Protocol Set will be finalized prior to database lock.
Safety Set	The Safety Set consists of all randomized subjects who received at least 1 dose of study drug.
Pharmacokinetic Set	The Pharmacokinetic Set consists of all randomized subjects who received at least 1 dose of etrasimod and with at least 1 postdose PK measurement.

11.4. Handling of Dropouts and Missing Data

All available data will be presented in descriptive summaries and included in statistical models as appropriate. All subjects who are included in the full analysis set (FAS), modified FAS (mFAS), Safety Set, or Pharmacokinetic Set will be included in analyses, and their missing data will not be imputed. For dichotomous efficacy endpoints, subjects with missing data for any reason will be considered as a ‘non-responder’ or ‘failure’.

11.5. Demographics and Baseline Characteristics

Demographics and Baseline characteristics will be summarized for the FAS and Safety Set. The summaries of data will include frequencies and percentages for categorical variables and mean, SD, median, minimum, and maximum for continuous variables.

11.6. Efficacy Analyses

The primary and secondary endpoints will be analyzed using the FAS. The exploratory endpoints will be analyzed using the FAS and the Randomized Set. Other important statistical

considerations, such as missing data imputation strategies, sensitivity analyses, and subgroup analyses will be described in the SAP.

The primary endpoint of percent change from Baseline to Week 24 in SALT I will be analyzed with a mixed-effects model repeated measures (MMRM) model. The MMRM model will include treatment group, visit, and interaction of treatment-by-visit as factors, and disease duration and Baseline SALT I score as covariates. An unstructured covariance matrix will be specified for the MMRM model. Least squares (LS) means at each visit and LS mean differences between treatment groups (each of the active arms versus placebo only) with p-values and corresponding 95% confidence intervals (CIs) will be reported. This method will also be applied to other score-based or continuous measures.

Proportion-based secondary endpoints at Week 24 will be analyzed using the Cochran-Mantel-Haenszel test method adjusted for the randomization stratification factor SALT I (< 50 , ≥ 50) at Baseline. Subjects with missing data for any reason will be considered as 'non-responder' or 'failure' for the endpoint. The number and percentage of subjects achieving the goal and the difference in proportion between treatment groups achieving the goal, along with p-values and the 95% CIs, will be reported.

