5.2 Adjustments for Covariates

For the continuous efficacy endpoints (e.g., change and percent change from baseline), disease duration and baseline value will be included as covariates in the statistical models, where disease duration, in years, will be calculated as follows:

$$\text{Disease duration (years)} = (\text{Randomization date} - \text{Initial onset date} + 1) / 365.25$$

Should the day be missing for the initial onset date, it will be imputed to the 1st of the month. Should both the day and month be missing for the initial onset date, they will be imputed to January 1st. Completely missing initial onset date will not be imputed.

For binary efficacy endpoints, Cochran-Mantel-Haenszel (CMH) tests will be stratified by the stratification factor for SALT I based on the value used by the IWRS at the time of randomization. If there are more than 10% of subjects who were mis-stratified, a sensitivity analysis will be conducted using the value from the clinical database.

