10.1 Primary Efficacy Endpoint

The primary efficacy endpoint is percent change from Baseline in SALT I at Week 24.

SALT I is a well-validated metric and widely utilized tool for determining the degree of hair loss based on the percentage of scalp surface area involved on the top, back, and each side of the scalp for AA. Using the diagram in [Figure 2](#), the Investigator will determine the percent scalp hair loss in a given quadrant, multiply this by the total scalp area delineated by that quadrant, and sum the resultant numbers for each quadrant to give the total percent scalp hair loss with a maximum score of 100. Change and percent change from Baseline in total percent of scalp hair loss will then be calculated as described in [Section 4.1](#).

Figure 2: Visual Aid for Estimating Percentage Scalp Hair Loss Using the Severity of Alopecia Tool

Analysis of Primary Efficacy Endpoint

Primary Analysis

Missing data will be handled as described in Section 5.3.

Percent change from baseline in SALT I score will be summarized using descriptive statistics by visit and treatment group. Observed and change from Baseline in SALT I score will be summarized similarly.

The primary endpoint will be analyzed using a MMRM model. The MMRM model will include the treatment group (2 mg, 3 mg, and placebo), analysis visit (Weeks 1, 2, 4, 8, 12, 16, 20, and 24), and treatment-by-analysis visit interaction as fixed effects, and disease duration (years; refer to Section 5.2) and Baseline SALT I score as covariates.

An unstructured (UN) variance-covariance matrix will be specified for the MMRM model. If convergence issues arise, the autoregressive (order 1) [AR(1)] structure will be used. If the AR(1) structure also does not converge, other covariance structures deemed appropriate to fit the data will be used and the structure with the smallest finite-sample corrected Akaike

Information Criteria (AAIC) value will be retained. Least squares (LS) mean estimates, LS mean differences between treatment groups (each of the active arms versus placebo only), corresponding 95% CIs, and p-values will be reported for each visit. The primary comparisons of interest will be between each active arm and placebo at Week 24.

Sensitivity Analysis

In addition to the primary analysis, the following sensitivity analyses will be performed using imputed data or alternative analysis set:

1) ANCOVA at Week 24 with Multiple imputation (MI) using the FAS

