AASIS Symptoms Sub-score (1-7): If at least 4 out of 7 symptom items i.e., AASIS (1-7) questions have been answered, then AASIS symptoms sub-score will be the arithmetic mean of all answered symptom items; otherwise, the sub-score will be set to missing.

AASIS Interference Sub-score (8-13): If at least 3 out of 6 interference items i.e., AASIS (8-13) questions have been answered, then AASIS interference sub-score will be the arithmetic mean of all answered interference items; otherwise, the sub-score will be set to missing.

AASIS Total Score: If both AASIS Symptoms Sub-score (1-7) and AASIS Interference Sub-score (8-13) are not missing, then AASIS total score will be the arithmetic mean of all answered symptoms and interference items, otherwise the total score will be set to missing.

AASIS exploratory efficacy endpoint is:

- Change from Baseline in AASIS at Week 24

AA-QLI

The AA-QLI is a disease-specific questionnaire developed to evaluate the impact of AA on quality of life. The AA-QLI has been validated with the Dermatology Life Quality Index and shown to provide more comprehensive insights about psychological distress among AA patients specifically. The AA-QLI consists of 21 questions covering 3 areas of daily life: subjective symptoms, relationships, and objective signs. AA-QLI Total Score is derived as the sum of the scores for the 21 questions. The results are presented on a scale varying between 21 and 84; a score

of 21 represents the best quality of life, while a score of 84 represents the poorest quality of life outcomes. AA-QLI Total Score will be set to missing if at least one question is not answered.

AA-QLI exploratory efficacy endpoint is:

- Change from Baseline in AA-QLI at Week 24

Lymphocyte Counts and Infections

Clinical safety laboratory tests will be completed predose at each study visit.

Lymphocyte counts exploratory efficacy endpoint is:

- Percent change from Baseline in peripheral lymphocyte counts at Week 24

Exploratory Endpoint Analyses

Main Analysis

With the following exception, exploratory efficacy endpoints will be summarized and analyzed as for the main analysis of the secondary efficacy endpoints (refer to Section 10.2).

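### The baseline covariate for AASIS, AA-QLI and lymphocyte counts is specified in two ways: Baseline SALT I by cross-reference, and most naturally each measure's own baseline in SAP 5.2

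*Protocol*

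**What the plan says.** Protocol 11.6 (repeated in the synopsis) describes the MMRM for percent change in SALT I, with "disease duration and Baseline SALT I score as covariates". It closes that paragraph with: "This method will also be applied to other score-based or continuous measures". No change of covariate is mentioned for those other measures.

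The SAP arrives at the same place by cross-reference. Section 10.3 covers AASIS, AA-QLI and lymphocyte counts and states that, with one exception, "exploratory efficacy endpoints will be summarized and analyzed as for the main analysis of the secondary efficacy endpoints". Section 10.2 analyses its continuous endpoint as in the primary analysis. Section 10.1 lists "disease duration (years; refer to Section 5.2) and Baseline SALT I score as covariates". The one exception in 10.3 concerns SALT I read by central review. Section 10.4 passes the same analysis on to AASIS and AA-QLI at Week 12 and to lymphocyte counts at the earlier visits.

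SAP 5.2, the section on covariate adjustment, gives a general rule for continuous efficacy endpoints: "disease duration and baseline value will be included as covariates in the statistical models". It does not say whose baseline.

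Table 3 of the SAP names only the analysis set, the missing-data approach and the model type for these endpoints. Section 12, which lists departures from the protocol, has no entry on covariates.

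**The concern.** For a SALT I endpoint, Baseline SALT I and the endpoint's own baseline are the same variable, so the two wordings agree. For a symptom score, a quality-of-life score or a lymphocyte count they are different variables. A programmer who follows 10.3 to 10.2 to 10.1 enters scalp hair loss as the baseline covariate; one who follows 5.2 enters the measure's own starting value. The two models give different LS mean differences, confidence intervals and p-values.

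A change from baseline is normally related to its own baseline. Leaving that baseline out costs precision. It also leaves uncorrected any chance difference between arms in that baseline, in favour of the arm that happened to start worse. With no formal testing strategy (SAP 5.6), the estimates and intervals are the result, and the choice between the two models should not remain open until the data are unblinded.

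**Working it through.** **The plan's own figure.** The only stated precision figure is the power for the primary endpoint (Protocol 11.2): "at least 80% and 47% power to detect a treatment difference of 20" percentage points, "using a 2-sided significance test level of 0.05 and common standard deviation (SD) of 17.8" percent, with "20 subjects to etrasimod 3 mg, 5 subjects to etrasimod 2 mg, and 10 subjects to placebo from Cohort 2". Two-sample t-test, noncentral t distribution:

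- 3 mg vs placebo: noncentrality 20 / (17.8 × √(1/20 + 1/10)) = 2.90, 28 df, power 79.97% (stated 80%).
- 2 mg vs placebo: noncentrality 20 / (17.8 × √(1/5 + 1/10)) = 2.05, 13 df, power 47.6% (stated 47%).

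Both reproduce. They concern SALT I only and do not depend on this point. The documents give no SD, correlation or power for AASIS, AA-QLI or lymphocyte counts, so what follows rests on assumed correlations.

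**Precision for a change score (AASIS, AA-QLI).** Let ρ be the correlation of the measure's own baseline with its Week 24 value, and r the correlation of that baseline with Baseline SALT I. Take equal variances at both times, and let Baseline SALT I be related to the Week 24 value only through the own baseline. In units of the outcome variance:

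- residual variance of change given Baseline SALT I: 2(1 − ρ) − r²(1 − ρ)²
- residual variance of change given own baseline: 1 − ρ²
- ratio of CI widths: √{[2(1 − ρ) − r²(1 − ρ)²] / (1 − ρ²)}, which is √[2/(1 + ρ)] when r = 0

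| ρ (assumed) | r = 0 | r = 0.3 | Simulation, 20 vs 10, r = 0 | Simulation, 20 vs 10, r = 0.3 |
|---|---|---|---|---|
| 0.3 | 1.240 | 1.221 | 1.241 | 1.221 |
| 0.5 | 1.155 | 1.142 | 1.161 | 1.142 |
| 0.7 | 1.085 | 1.077 | 1.086 | 1.074 |
| 0.9 | 1.026 | 1.024 | 1.028 | 1.025 |

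The simulation is a single-visit ANCOVA with disease duration in both models, 2,000 runs per setting; it is not the full MMRM. Arms of 20 vs 20 gave similar ratios. In no setting was the SALT I-adjusted interval the narrower one.

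The same result in terms of information: with r = 0, the SALT I-adjusted analysis carries a fraction (1 + ρ)/2 of the information of the own-baseline analysis. At ρ = 0.6 that is 0.80, a loss of one fifth.

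**Chance imbalance.** With r = 0 and the own baseline left out, a baseline difference of d SD between arms shifts the difference in change by (1 − ρ)d. At ρ = 0.6 and d = 0.5 the shift is 0.4 × 0.5 = 0.2 SD. How unusual d = 0.5 is depends on arm size:

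- 24 vs 24 (3 mg vs pooled placebo as randomized): SE = √(1/24 + 1/24) = 0.29, so 0.5 SD is 1.7 SE.
- 20 vs 10 (Cohort 2 completers): SE = √(1/20 + 1/10) = 0.39, so 0.5 SD is 1.3 SE.

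Across all simulated change-score settings the mean SALT I-adjusted estimate under no effect lay between −0.015 and 0.015 SD. There is no bias over repeated randomization.

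**Lymphocyte percent change.** Simulated separately at 20 vs 10, assuming a log-scale SD of 0.3, a halving of counts on active treatment and r = 0. The CI-width ratios were 1.168, 1.114, 1.065 and 1.021 at log-scale correlations of 0.3, 0.5, 0.7 and 0.9. If Week 24 counts are strictly proportional to baseline, the ratio is 1.00 and nothing is lost.

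**The case against.** The strongest reply is that SAP 5.2 already gives the rule. It is the section on covariates, it speaks of change and percent change generally, and its wording is most naturally read as the baseline of the endpoint analysed. On that view 10.1 is simply the rule applied to SALT I. The cross-reference chain cannot be meant literally anyway: the model in 10.1 lists Weeks 1, 2, 4, 8, 12, 16, 20 and 24, whereas in the double-blind period AASIS and AA-QLI are collected only on Day 1, Week 12 and Week 24. So the reference must mean the same method with endpoint-specific details. Protocol 11.1 also leaves analysis detail to the SAP.

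Much of this stands. A reader might infer that the plan definitely adjusts these endpoints for the wrong baseline. The documents do not support that: no passage names Baseline SALT I specifically for AASIS, AA-QLI or lymphocyte counts, and 5.2 points the other way. What the reply does not do is settle the matter in writing. Section 5.2 does not say whose baseline, 10.3 states an exception without mentioning this one, and neither Table 3 nor Section 12 helps.

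It is also fair to say that the endpoints are exploratory or other, and that every figure above on loss of precision depends on assumed correlations.

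**Conclusion.** The covariate for AASIS, AA-QLI and lymphocyte counts is specified in two ways, and the plan should choose one. Any loss is conditional on which wording is followed:

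- **SALT I wording:** intervals about 2–24% wider for AASIS and AA-QLI change (ρ from 0.9 down to 0.3, r of 0 or 0.3) and about 0–17% wider for lymphocyte percent change, with no correction for chance imbalance in the measure's own baseline.
- **Own baseline, the natural reading of SAP 5.2:** no loss.

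Two stronger conclusions are not supported. A reader might infer that the treatment estimates would be biased; they are unbiased over repeated randomization, and the imbalance shift is conditional on the baselines that happen to be observed. A reader might also infer that the main results are at risk. They are not: for the primary endpoint and the continuous secondary endpoint the two wordings name the same variable, the proportion endpoints use a stratified CMH test, and the stated power reproduces.

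**What to change.** In SAP 5.2 state that the baseline covariate is the Baseline value of the endpoint being analysed: AASIS, AA-QLI or lymphocyte count for those endpoints, and SALT I for SALT I endpoints. Refer to that sentence from 10.3. Baseline SALT I may be kept as an additional covariate if wanted. Record in SAP Section 12 that this supersedes the covariate wording of Protocol 11.6 for these measures.

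The cost is one sentence, one cross-reference, one row in the table of changes and one covariate in the programs. The questionnaires and laboratory tests are already scheduled on Day 1 in both cohorts, so no data, visits or subjects are added. The change should be made before the double-blind data are unblinded.
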